#### **7.1.1 Dosage Form, Preparation and Labeling**

The dosage (dilution) of PMA will be the same for all subjects and will begin with vial number #5 which will be prepared by serial five fold dilutions from the most concentrated vial (#1).

One PMA active treatment set will be prepared by compounding three separate concentrated vials (#1) each containing approximately 30 antigen mixtures (no more than about 75 total antigens each) and labeled mix A, B and C. No more than 0.9 ml of each manufacturer supplied stock material will be placed in a 100ml vial and brought to volume with diluent. Each of the #1 vials (A, B and C) will then be serially diluted 5 fold, several times approximately as follows:

	Mix A (Pollens)	Mix B (Indoor)	Mix C (Molds)	Exact Preparation
Vial #1	1:1	1:1	1:1	Described above
Vial #2	1:5	1:5	1:5	20ml Vial #1 + 85ml diluent
Vial #3	1:25	1:25	1:25	4ml Vial #1 + 85ml diluent
Vial #4	1:125	1:125	1:125	4ml Vial #2 + 85ml diluent
Vial #5	1:625	1:625	1:625	4ml Vial #3 + 85ml diluent

7.1.2 Vials #1-2 will have an expiration date of six months and dilutions #3-5 may be used for up to three months.

7.1.3 One placebo set will also be prepared in a similar manner using sterile saline and an equivalent amount of glycerin/phenol. Because up to 20% of patients receiving active treatment may notice local swelling and itch, histamine will be added to the stock placebo vials (vial 1) at a concentration of 50ug/ml (0.05mg/ml). Thus vial #2 will have a final concentration of 0.01mg/ml histamine. This is expected to elicit a mild itch in about 20% of control subjects based on experience.

Folic acid will also be added to the placebo vials to yield a slightly yellow color similar to the active treatment vials. Stock placebo (#1 vials) will contain 1mg/ml folic acid by adding 20ml of 5mg/ml folic acid to 80ml diluent. This will be further diluted 5 fold to yield (#2 vial) for a final concentration of 0.2mg/ml folic acid and so on.

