The labeling of study PMA and placebo solutions will be undertaken by the compounding pharmacy of this investigation and undertaken in conjunction with the sponsor so that a double-blind study technique can be employed during the investigation. Each active and placebo vial set will be labeled randomly either set I or II. The set, mix letter, dilution, and use by date will also be included as shown by the example below. Only the pharmacy and sponsor will hold the treatment set randomization code. Recruited subjects will alternate between sets I and II.

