#### *7.1.4 Immunotherapy Dose and Regimen*

Recruited subjects alternate to be assigned either treatment set I or II (representing either placebo or active PMA treatment in a binded fashion). The assigned treatment set will remain for the duration of the study for each subject. On the day of an injection, 0.3ml from each of the appropriate vial set mix (A-C) will be combined in a sterile 5 ml bottle. Using a new sterile syringe, 0.15-0.60ml of the PMA solution or placebo will be removed for injection purposes according to the injection schedule (Appendix I). A sterile 27G ½ inch syringe will be used for administration. Immunotherapy will be administered bi-weekly in the study clinic for a total of eight consecutive weeks. Appendix I lists the precise immunotherapy injection schedule.

All patients are required to remain in the clinic under close observation by the study nurse for a period of 30 minutes following their injection. A physician is required to be present in the clinic at all times. In addition, one of the investigators must be present on campus and available by cell phone during scheduled treatment sessions. Emergency medications such as albuterol, oxygen, diphenhydramine, and at least two epi-pens will be readily available in the treatment area.

It is important to note that the maximum concentration of each individual allergen is quite low compared to more traditional immunotherapy regimens. The maximum PNU/ml (Protein Nitrogen Units) in vial #1 will be no more than about 180 PNU/ml per allergen (eg 0.9ml of 20,000 PNU/ml stock material into 100ml solution). In most cases the actual concentration of each stock allergen is much lower than 20,000 PNU/ml since the material may be provided as a mixture of several allergens. We would estimate therefore that subjects would receive no more than about 7.2 PNU of antigen contained in the highest injection (0.2ml Vial #2). Typically, allergens are administered via immunotherapy in a range of about 2000 PNU. Thus the dosage of each allergen is less than 0.36% of a typical dose administered in our clinics. The lower overall dosing scheme provided in this study would therefore be considered to be extremely safe with minimal adverse events.

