### **7.3 Unblinding Procedure**

The investigational drug blind shall not be broken by the investigator unless information concerning the investigational immunotherapy is necessary for the medical treatment of the subject. In the event of a medical emergency, if possible, the medical monitor should be contacted before the investigational immunotherapy blind is broken to discuss the need for unblinding.

For unblinding a subject, the investigational immunotherapy blind can be obtained by contacting the vendor compounding pharmacist. The sponsor must be notified as soon as possible if the investigational immunotherapy blind is broken. The date, time, and reason the blind is broken must be recorded in the study subject's source documents and the same information must be recorded on the subject's CRF. Investigational immunotherapy must be stopped immediately and the subject must be withdrawn from the study.

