  - e) that the subject's identity will remain confidential in the event that study results are published.
24. Female subjects of childbearing potential (eg, nonsterilized, premenopausal female subjects) who are sexually active must use adequate contraception (as defined in the informed consent) from Screening throughout the duration of the study. Regular pregnancy tests will be

performed throughout the study for all female subjects of childbearing potential. If a subject is found to be pregnant during study, study immunotherapy will be discontinued and the investigator will offer the subject the choice to receive unblinded treatment information.

25. Male subjects must use adequate contraception (as defined in the informed consent) from Screening throughout the duration of the study. If the partner or wife of the subject is found to be pregnant during the study, the investigator will offer the subject the choice to receive unblinded treatment information.
26. A statement that clinical trial information from this trial will be publicly disclosed in a publicly accessible website, such as ClinicalTrials.gov.

---

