## Appendix I Allergy Rescue Medication Action Plan

Ask patient if symptoms are adequately controlled at each bi-weekly visit. The response dictates whether a medication is added or subtracted. Resuce medications will not be increased after week 10.

Symptoms Controlled?	Medication Action
no	Add medication
yes	Subtract medication

Step	Rescue Medication	Score
A	None	0 points
B	Loratadine 10mg PO Daily	1 point
C	Loratadine 10mg PO BID	2 points
D	Loratadine BID plus Triamcinolone Daily	4 points
E	Loratadine BID plus Triamcinolone BID	6 points
F	Loratadine BID plus Triamcinolone BID plus Prednisone 5mg Daily	9 points
G	Loratadine BID plus Triamcinolone BID plus Prednisone 5mg BID	12 points

**Note:** To calculate the daily medication score add the total points for all medications noted above. Any other allergy rescue medications inadvertently added will also be counted in a similar manner as follows; other oral antihistamines (1 points each tablet), ophthalmic allergy medications (1 points each use), other nasal steroids, cromolyn, azelastine (2 points daily, 4 points BID). Symptoms and medication use are recorded daily at home.

---

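### Two vial labels that map one-to-one to arm, with alternating assignment, let a single code break reveal every subject's treatment to site staff

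*Combined protocol and SAP*

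**What the plan says.** Section 7.1.1 describes one active treatment set and then one placebo set: "One placebo set will also be prepared in a similar manner using sterile saline and an equivalent amount of glycerin/phenol". On labelling it says "Each active and placebo vial set will be labeled randomly either set I or II" and "The set, mix letter, dilution, and use by date will also be included as shown by the example below". The Figure 7.a example shows set, dilution, mix, company and use-by date, with no subject-level code. The same section has recruited subjects alternate between the sets and reserves the code to the pharmacy and the sponsor.

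Section 7.1.4 repeats the alternation and says what the labels mean: "Recruited subjects alternate to be assigned either treatment set I or II (representing either placebo or active PMA treatment in a binded fashion". It adds: "The assigned treatment set will remain for the duration of the study for each subject". The SAP names its comparison groups I and II for every outcome.

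The plan foresees disclosures. Under section 7.3, when the investigator needs the information for a subject's medical treatment, "the investigational immunotherapy blind can be obtained by contacting the vendor compounding pharmacist". Only that subject is withdrawn, and nothing is said about the others on the same set. Under Appendix C items 24 and 25, if a subject or a male subject's partner becomes pregnant, "the investigator will offer the subject the choice to receive unblinded treatment information". Section 8.1.10 makes pregnancy reporting and follow-up depend on the arm.

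On rescue medication, Appendix I has staff ask at each bi-weekly visit whether symptoms are controlled, and "The response dictates whether a medication is added or subtracted". Section 12.1.3 adds the average medication score to the average nasal symptom score to form the DCS, a primary outcome.

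**The concern.** Section 7.3 is written as if the blind could be broken for one subject, but the code has only two values for the whole trial. Telling an investigator that one subject on set II has active treatment also tells that investigator about every other set II subject and, by elimination, every set I subject.

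This is a single-site trial. Investigators or their designees give every dose (section 5.1), and section 8.1 asks for the same personnel whenever possible. The people who learn the code may well be those who run the remaining visits. The primary outcomes, DCS and mini-RQLQ, are subject-reported. Staff who know the arm could shade how they ask about symptom control or explain a questionnaire, for every subject still on study. With 36 subjects, even modest drift by arm could matter, and a disclosure cannot be undone.

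A weaker leak needs no code break. Staff see about 18 subjects under each label and are asked at each visit which treatment they think is being given (section 12.1.3). They can pool impressions by set, so their guesses are not independent across subjects.

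**Working it through.** **The plan's own figure.** The leak depends only on the number of subjects, 36 recruited to cover 28 needed (section 12.3). The 28 reproduces from 80% against 30%, two-sided 0.05 and 80% power by the arcsine formula:

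- h = 2·asin(√0.8) − 2·asin(√0.3) = 2.214 − 1.159 = 1.055
- n per arm = 2 × ((1.960 + 0.842)/1.055)² = 14.1, so 28.2 in total

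**How many assignments one break determines**

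| Coding | Assignment order | Subjects whose arm is revealed |
|---|---|---|
| Set I / set II (as planned) | any | 36 of 36 |
| Subject-specific codes | alternating | 36 of 36, by odd or even place in enrolment |
| Six codes, three per arm | alternating | 36 of 36, for the same reason |
| Six codes, three per arm | concealed random list | about 36/6 = 6 |
| Subject-specific codes | concealed random list | 1 |

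The second and third rows matter. Under strict alternation, one known arm at one known place in the sequence fixes all the others. New codes therefore do not help unless alternation goes too. The protocol is also inconsistent here: section 5.1 claims computerized random assignment and section 7.2 a pharmacy randomization schedule, while sections 7.1.1 and 7.1.4 say subjects alternate. If the section 7.2 list is what is really used, enrolment order no longer leaks, but the two labels still do.

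**Chance of at least one break.** The documents give no rate, so q, the per-subject probability of a code break, is an assumption. P = 1 − (1 − q)^36:

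| q (assumed) | P |
|---|---|
| 0.1% | 1 − 0.999^36 = 3.5% |
| 0.5% | 1 − 0.995^36 = 16.5% |
| 1% | 1 − 0.99^36 = 30.4% |
| 2% | 1 − 0.98^36 = 51.7% |
| 5% | 1 − 0.95^36 = 84.2% |

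**Labelling cost.** Vials #2 to #5 are injected (Appendix H): 4 dilutions × 3 mixes = 12 labelled vials per code. Two codes need 24, six need 72, and 36 subject codes need 12 × 36 = 432 small aliquots, per preparation. Volume is not the constraint. Section 7.1.4 draws 0.3 ml of each mix per visit and each dilution is used at four visits, so 18 subjects use 0.3 × 4 × 18 = 21.6 ml. The preparation table gives 4 + 85 = 89 ml or 20 + 85 = 105 ml per diluted vial.

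**The case against.** - **The break rate could be very low.** Section 7.3 allows a break only when treatment requires it. Section 9.1.4 reports no anaphylaxis or serious systemic reaction in more than 20,000 patients. At face value, the rule of three gives an upper bound of 3/20,000 = 0.015% per patient, or about 36 × 0.015% = 0.5% across the trial. That experience is uncontrolled and covers neither other emergencies nor pregnancy. Pregnant women and those intending pregnancy are excluded, contraception is required, and unblinding for pregnancy is the subject's choice. This stands as a reason to include low rates and give the 84% no special weight.
- **Staff do not choose the rescue step.** A reader might infer that they do. Appendix I does not support this: the subject's yes or no moves the step along a fixed ladder, and rescue is not increased after week 10. Symptom and medication cards are completed at home, and the mini-RQLQ is answered by the subject. What remains is influence through asking, recording and applying the answer.
- **Whoever learns the code may not run visits.** The documents do not say that this is the same person, and section 7.3 requires only the date, time and reason of the break to be recorded. The overlap is a reasonable inference at one site, not a stated fact.
- **Safeguards exist.** The code sits with pharmacy and sponsor, the placebo carries histamine, glycerin, phenol and folic acid to mimic the active vials, and treatment guesses are collected at each visit. These reduce what can be learned by pooling, and the guesses may show that the blind was lost. None limits what a formal break reveals.
- **Other identifiers are mentioned.** Section 7.2 refers to an immunotherapy ID number and Appendix J to a vial ID. Whatever they are, the set name remains on the label.

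**Conclusion.** The structural point holds. As written, one code break reveals 36 of 36 assignments to site staff who know the set labels or the enrolment order. This follows from sections 7.1.1, 7.1.4 and 7.3 and needs no assumed rate. How likely a break is does rest on an assumption: about 4% to 84% for per-subject rates of 0.1% to 5%.

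A reader might infer that a break would bias all 36 subjects. The documents do not support that. Scores already recorded cannot change, so only subjects with outcomes still to come are at risk. Their number depends on the timing of the break and the overlap of enrolment, which the plan does not state. Nor do the documents show that the blind is lost from the start; the harm is conditional on a disclosure. It should nevertheless be fixed before enrolment, because it is cheap to prevent and cannot be repaired afterwards.

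**What to change.** 1. In sections 7.1.1 and 7.1.4 and Figure 7.a, replace set I and set II with subject-specific codes. Failing that, use several codes per arm, for example three active and three placebo with about 6 subjects each, which limits a break to that code's subjects.
2. In the same sections, delete the sentences that have subjects alternate and rely on the concealed computerized list that sections 5.1 and 7.2 already claim. Both changes are needed together.
3. In section 7.3, have the pharmacist release treatment for the affected subject's code only.
4. In the SAP, name the comparison groups by treatment, not I and II, with the link to treatment applied after database lock.

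The cost is pharmacy labelling and slightly more accountability work. Six codes need 72 labelled vials against 24 per preparation. Both counts repeat whenever dilutions expire, and section 7.1.1 gives vials #3 to #5 up to three months. Subject-specific codes need more, smaller aliquots. Doses, visits and number of subjects do not change.

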## **5.0 STUDY DESIGN AND METHODS**

### **5.1 Study Design**

This is a phase 2 proof of concept study. It is being undertaken to characterize and quantify the clinical difference in signs and symptoms that may evolve when subjects with active SAR/PAR are administered a sub-cutaneous form of immunotherapy in a double-blind, prospective, controlled six weeks study wherein a PMA is compared with saline placebo.

Randomization to active PMA versus placebo treatment is on a 1 to 1 ratio. A double-blind study design is used to minimize outcome bias. Randomization measures to minimize bias at study entry include computerized random assignment of treatment versus placebo vials.

Subjects who are receiving nasal steroids for their SAR/PAR at screening may continue in the screening process if they agree to discontinue their therapy and commence a 14 day wash-out period of their medication prior to receiving active/placebo immunotherapy. Potential study subjects who, at screening, are not on active treatment for their SAR/PAR and asthma may enter directly into the investigation provided they fulfil entry and exclusion criteria and screening testing requirements.

The population to be studied consists of male and female adults aged 18 years to 65 years who are actively manifesting SAR/PAR have a score of at least 28 on the mini-RQLQ and 6 on the TNSS scale.

[figure not shown]
The active treatment phase of the study will be for six weeks with a safety followup assessment at 30 days post-treatment. No interim analysis is planned.

The study immunotherapy that will be evaluated in this study is a new innovative proprietary mixture of FDA approved allergens which has been clinically developed and evaluated, during the past three decades, in some 20,000 patients by the inventor of the mixture (see 3.2). In clinical evaluation this patented antigen mixture has provided clinical symptomatic relief to patients with SAR/PAR in as brief a period as three administrations of immunotherapy injections and has an observed overall success rate of approximately 80 to 90 percent of such treated subjects.

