### **6.1 Inclusion Criteria**

1. In the opinion of the investigator, the subject is capable of understanding and complying with protocol requirements.
2. The subject signs and dates a written, informed consent form prior to the initiation of any study procedures.
3. The subject is a male or a non-pregnant, non-lactating female between the ages of 18 and 65.
4. The study subject is currently experiencing active symptoms and signs of moderate to severe PAR with or without SAR component defined as score of at least 28 on the RQLQ and 6 on the TNSS scale. Scores will be determined on the first and second visit (after the 14 day medication washout period). Both scores exceeding their threshold on either day will qualify.
5. Skin test strongly positive (wheal at least 5mm diameter and 2mm greater than negative control) to at least 6 of 48 allergy skin prick tests including at least one species of dust mite.

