### 7.2 Investigational drug Assignment and Dispensing Procedures

A study subject randomization schedule will be developed by the study vendor compounding pharmacy or designee. In addition, stratification of study subject entry into the investigation will be determined by the study site investigators correlated with the study subject's clinical entry diagnostic criteria (see 6.1).

Subjects will be assigned to receive their treatment according to the randomization schedule provided to the study site by the vendor compounding pharmacy. The immunotherapy ID Number will be entered onto the study subject's CRF. All study immunotherapy will be administered to the study subjects while they are in the study site clinic.

Investigational immunotherapy blind maintenance will be undertaken by the vendor compounding pharmacy. During regularly scheduled monitoring visits, a study monitor from the sponsor or a designee will perform an inventory of blinded investigational immunotherapy solutions. All

unassigned treatment immunotherapy solutions will be reconciled and returned to the sponsor or a designee before study closure.

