#### **8.3.2 Study Entrance Randomization**

Study Randomization will take place on study day 1 (Visit 1). The following procedures will be performed and documented during Study Randomization:

- If the subject has satisfied all of the inclusion criteria and none of the exclusion criteria for randomization and the investigator deems the laboratory screening and skin testing are acceptable for continuance in the investigation, the subject should be randomized using the randomization sequence provided by the sponsor.
- Subjects will receive their first sub-cutaneous administration of immunotherapy with dose vial #5.
- The procedure for documenting Screening failures is provided in Section 8.1.11.

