## **Appendix C Elements of the Subject Informed Consent**

In seeking informed consent, the following information shall be provided to each subject:

1. A statement that the study involves research.
2. An explanation of the purposes of the research.
3. The expected duration of the subject's participation.
4. A description of the procedures to be followed, including invasive procedures.
5. The identification of any procedures that are experimental.
6. The estimated number of subjects involved in the study.
7. A description of the subject's responsibilities.
8. A description of the conduct of the study.
9. A statement describing the immunotherapy treatment and the probability for random assignment to each treatment.
10. A description of the possible side effects of the treatment that the subject may receive.
11. A description of any reasonably foreseeable risks or discomforts to the subject and, when applicable, to an embryo, fetus, or nursing infant.
12. A description of any benefits to the subject or to others that reasonably may be expected from the research.
13. Disclosures of appropriate alternative procedures or courses of treatment, if any, that might be advantageous to the subject and their important potential risks and benefits.
14. A statement describing the extent to which confidentiality of records identifying the subject will be maintained, and a note of the possibility that regulatory agencies, auditor(s), IRB, and the monitor may inspect the records. By signing a written informed consent form, the subject or the subject's legally acceptable representative is authorizing such access.
15. For research involving more than minimal risk, an explanation as to whether any compensation and an explanation as to whether any medical treatments are available if injury occurs and, if so, what they consist of or where further information may be obtained.
16. The anticipated prorated payment(s), if any, to the subject for participating in the study.
17. The anticipated expenses, if any, to the subject for participating in the study.
18. An explanation of how to contact the investigators or designees for answers to pertinent questions about the research, subject's rights, and IRB and whom to contact in the event of a research-related injury to the subject.

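### Sections 7.1.1 and 7.1.4 assign subjects by alternating between two vial sets, which cannot be squared with the subject-level randomisation in 5.1, 7.2, 8.3.2 and the SAP

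*Combined protocol and SAP*

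**What the plan says.** The protocol gives three different rules for deciding which treatment a subject receives.

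- **Alternation.** Section 7.1.1: "Recruited subjects will alternate between sets I and II". Section 7.1.4: "Recruited subjects alternate to be assigned either treatment set I or II". The random step described in 7.1.1 is the labelling of the active and placebo vial sets as I or II. Only the pharmacy and the sponsor hold that code.
- **A pharmacy schedule.** Section 7.2: "Subjects will be assigned to receive their treatment according to the randomization schedule provided to the study site by the vendor compounding pharmacy". The same section adds a stratification, to be determined by the site investigators and tied to the entry criteria in 6.1.
- **A sponsor sequence.** Section 8.3.2: "the subject should be randomized using the randomization sequence provided by the sponsor".

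Section 5.1 and the SAP's study design section both say that about 36 subjects are randomised equally to the two arms. Both also contain the sentence "Randomization measures to minimize bias at study entry include computerized random assignment of treatment versus placebo vials". Appendix C, item 9, requires the consent form to describe "the probability for random assignment to each treatment".

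**The concern.** Alternation is a deterministic rule. Once the first subject has been given a set, every later assignment is fixed and visible in advance to anyone who knows the last one. A site that follows 7.1.1 and 7.1.4 is not running the randomised trial described in 5.1 and the SAP, and the consent statement on random assignment would be inaccurate.

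The practical risk is selection at entry. Inclusion criterion 1 and exclusion criterion 3 rest on the investigator's opinion, so there is room to enter, defer or decline a subject. Each arm has a single set label, printed on the vials and kept by each subject throughout, so staff impressions of a set can accumulate over all subjects using it. Section 12.1.3 has patients and staff asked for their guess at treatment, with the answers recorded at each visit. The efficacy measures are self-reported symptoms and quality of life, plus rescue medication stepped according to whether the patient feels controlled. A difference between arms created at entry could not be separated from a treatment effect afterwards.

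**Working it through.** **1. Can the rules be reconciled?** The sentence on computerised assignment in 5.1 and the SAP refers to vials, so it could mean no more than the random labelling of the two sets. It is therefore weak evidence of conflict. The other statements cannot be read that way: 5.1 and the SAP randomise subjects, and 7.2 and 8.3.2 require a subject-level schedule or sequence. A subject cannot be assigned both by turn and from a random sequence. In addition, 7.2 and 8.3.2 name different sources for that sequence.

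**2. Inputs.** 36 subjects at 1:1 (section 5.1), hence 18 per arm. The guesser knows all past set labels, guesses the set with fewer subjects so far, and tosses a coin when the sets are level. Under alternation, the guesser names the other set after the first subject.

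**3. Number of possible label sequences.**
- Alternation: 2 (I first or II first).
- One random list of 18 and 18: C(36,18) = 9,075,135,300.
- Mixed blocks of 2 and 4 (an illustration; the documents give no block size): f(n) = 2f(n−2) + 2f(n−4), with f(0) = 1 and f(2) = 2, gives f(36) = 56,714,752.

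**4. Expected correct guesses of the next set label.**
- Alternation: 0.5 for the first subject plus 35 certain = 35.5; 35.5/36 = 98.6%.
- One 18+18 list: 18 + 2^35/C(36,18) − 0.5 = 18 + 3.79 − 0.5 = 21.3; 21.3/36 = 59%. Simulation gave 21.29.
- Mixed blocks of 2 and 4: simulation gave 25.93/36 = 72.0%. As a hand check, a block of 2 yields 1.5 correct and a block of 4 yields 2 + 8/6 − 0.5 = 2.83. With the two sizes equally likely, (1.5 + 2.83)/(2 + 4) = 72%.
- Independent coin tosses: 18/36 = 50%.

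**5. Sample size.** The plan's 28 evaluable subjects for 80% against 30% is approximately reproduced. The pooled two-sided normal formula gives 15 per arm (30 in total), and 14 per arm has 79.1% power. Going from 28 to 36 implies 1 − 28/36 = 22.2% dropout. None of this depends on how the list is generated, so the sample size does not change.

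**6. Visit numbering.** Section 8.3.2 places randomisation and the first administration at Visit 1. Inclusion criterion 4 is scored at the first and second visits, the second after washout, and can be met at either. Section 9.2.1.1 and Appendix H place the first injection at visit 2. These statements conflict and must be reconciled.

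**The case against.** The best defence is that knowing the next label is not knowing the next treatment. The code stays with the pharmacy and the sponsor. The placebo is matched with glycerin and phenol, histamine and folic acid. The sets are labelled at random. This stands as far as it goes: every prediction figure above concerns labels. It does not rescue alternation, because a mistaken belief about the sets can unbalance the arms as easily as a correct one, and because the documents claim subject-level randomisation.

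Several stronger readings are tempting, and the documents do not support them.

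- A reader might infer from the Visit 1 timing that subjects would be assigned before eligibility is confirmed. Section 8.3.2 itself randomises only subjects who satisfy all criteria, 8.1.12 agrees, and section 6.0 requires confirmation before the first dose. What remains is a visit-numbering conflict.
- A reader might infer that two possible sequences invalidate the planned p-values. That limit belongs to a randomisation test, whereas the SAP plans unpaired t tests for the primary outcomes.
- A reader might infer that the stratification in 7.2 has no basis at all. It points to the entry criteria in 6.1, but gives no usable strata.
- A reader might take the SAP's comparison of groups I and II as an error. With one set per arm, these are simply the arms under blinded names.

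**Conclusion.** The contradiction is real and needs correction before enrolment, because predictable assignment cannot be repaired afterwards. Sections 7.1.1 and 7.1.4 describe a non-random sequence with two possible forms. The next set label is known for 35 of 36 subjects, with 98.6% expected correct guesses against about 59% for a single random list. The figures assume exactly 36 subjects, 18 per arm, and an enroller who sees past labels. How much bias would follow cannot be calculated from the documents, since it depends on whether staff form a view about the sets and act on it. The visit numbering and the undefined strata are lesser points.

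A separate matter, outside the required correction, is that one visible label serves each whole arm. If a single unblinding reached blinded staff, the other 17 subjects on that set would be known directly and the 18 on the other set by elimination, 35 of 35. This would hold under perfect randomisation too, and the documents give no probability of it happening.

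**What to change.** 1. Delete the alternation sentences in 7.1.1 and 7.1.4.
2. Assign from one computer-generated 1:1 random list. Any concealed random list will do, for example a single 18+18 list or varying blocks whose sizes the site does not know. One named party outside the site team should hold it and release each assignment only after that subject's eligibility is confirmed.
3. Make 5.1, 7.2, 8.3.2 and the SAP's study design section name that same list and holder.
4. Reconcile the visit numbering in 8.3.2 with inclusion criterion 4, 9.2.1.1 and Appendix H. Give the stratification in 7.2 usable strata or remove it.

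The cost is a protocol amendment, a short SAP amendment and one list, with no extra subjects or visits.

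Optional: use several pharmacy-applied codes per arm, with use-by dates that do not differ by arm. With three equal codes per arm (six subjects each), one unblinding reveals 5 others, and the remaining 30 can be guessed at 18/30 = 60%. Labelled working vials per fill rise from 2 codes × 3 mixes × 4 dilutions = 24 to 6 × 3 × 4 = 72. Only if this is adopted do the references to groups I and II in 12.1.3 and the SAP need rewording.
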